### 9.4.1.1.1. Dose Adjustments

#### 9.4.1.1.1.1. Blinded Study Drug

Blinded study drug dose adjustments are allowed both within a cycle and between cycles. Blinded study drug must be reduced as outlined in Table JPBQ.9.3.

For patients requiring dose reduction(s), re-escalation to a prior dose level is permitted only after consultation with the Lilly CRP.

**Table JPBQ.9.3. Dose Adjustments for Abemaciclib**

Dose Adjustment	Oral Dose	Frequency
0	150 mg	Q12H
1	100 mg	Q12H
2	50 mg	Q12H

Abbreviation: Q12H = every 12 hours.

Blinded study drug must be discontinued if further dose reduction is required beyond 50 mg Q12H. If a patient who, in the judgment of the investigator, is receiving clinical benefit from study therapy requires further dose reduction than is outlined in Table JPBQ.9.3, then the investigator must discuss with the Lilly CRP prior to any further dose reduction.

In the event that blinded study drug must be discontinued, a patient may continue to receive anastrozole, letrozole, or fulvestrant.

**9.4.1.1.1.2. NSAID/Fulvestrant**

Per NSAID labels, dose adjustment for anastrozole or letrozole is not applicable, as only a single-dose strength is approved for each medication. In exceptional cases, or in the absence of evidence of PD, the investigator may discuss a change in the specific NSAID administration (eg, switching from anastrozole to letrozole) with the Lilly CRP. In the event that anastrozole or letrozole must be discontinued, a patient may continue to receive blinded study drug per the investigator's clinical judgment.

Dose adjustment for fulvestrant will be determined by the investigator in accordance with the label. For patients with moderate hepatic impairment (defined as Child-Pugh Class B), including any patient who develops moderate hepatic impairment during study treatment, fulvestrant 250 mg should be administered intramuscularly into the buttock slowly (1 to 2 minutes) as one 250-mg injection. In the event that fulvestrant must be discontinued, a patient may continue to receive blinded study drug.

**9.4.1.1.2. Dose Suspension (within a Cycle) and Cycle Delay**

Both dose suspension (within a cycle) and cycle delay are permitted. When a dose suspension or cycle delay occurs related to toxicity (defined as an AE possibly related to study treatment per investigator judgment), the blinded study drug and/or NSAID/fulvestrant may be suspended or delayed as determined by the investigator's judgment.

Study treatment may be held up to 14 days within a cycle or at start of next cycle to permit sufficient time for recovery from the toxicity. If a dose suspension occurs within a cycle, the investigator may resume blinded study drug dosing at the same dose level for the remainder of the cycle or at reduced dose (assuming resolution to at least Grade 1 for non-hematological toxicity and at least Grade 2 for hematological toxicity). If the patient experiences the same toxicity with the same or greater severity (Common Terminology Criteria for Adverse Events [CTCAE] grade) requiring a dose suspension within a cycle or at start of the next cycle, the patient must be dose reduced and not re-challenged a second time at the prior dose level.

In the event of a dose suspension of blinded study drug during Cycle 1, fulvestrant may be administered as scheduled on Cycle 1 Day 15. If a toxicity possibly related to blinded study drug occurs prior to initiating the next cycle, fulvestrant may be administered and blinded study drug suspended until recovery from the toxicity.

If NSAID/fulvestrant is administered but blinded study drug is suspended, the date of NSAID/fulvestrant administration shall constitute Day 1 of the next cycle.

Patients not recovering from toxicity within 14 days should be considered for discontinuation of the blinded study drug and/or co-administered NSAID/fulvestrant. In exceptional circumstances, a delay >14 days is permitted upon agreement between the investigator and the Lilly CRP and blinded study drug dose adjustment is to be considered.

In the event of a cycle delay due to logistical reasons (eg, due to patient availability), the patient should continue on study treatment if the patient has adequate drug supply. If a patient's treatment is interrupted as a result of not having sufficient drug supply, the cycle may be delayed

up to 7 days (and not be considered a protocol violation). In exceptional circumstances, a delay >7 days is permitted upon agreement between the investigator and the Lilly CRP.

The start of a cycle may be delayed, or a current cycle interrupted, to allow a patient with locoregionally recurrent breast cancer rendered operable by study treatment to receive surgery ± radiotherapy. For additional information, refer to Section 9.6.1.

#### **9.4.1.1.3. Hematologic Toxicity**

If a patient experiences Grade 4 hematologic toxicity, then study treatment must be suspended (until the toxicity resolves to at least Grade 2) and the dose of blinded study drug must be reduced by 1 dose level as outlined in [Table JPBQ.9.3](#).

If a patient experiences Grade 3 hematologic toxicity, then study treatment must be suspended (until the toxicity resolves to at least Grade 2) and the dose of blinded study drug may be reduced by 1 dose level as outlined in [Table JPBQ.9.3](#) at the discretion of the investigator.

If the patient experiences a recurrent episode of Grade 3 hematologic toxicity within 8 weeks, then dosing must be suspended (until the toxicity resolves to at least Grade 2) and the dose of blinded study must be reduced by 1 dose level as outline in [Table JPBQ.9.3](#).

Recurrent toxicity refers to the same event occurring within the next 8 weeks (as measured from the stop date of the preceding event). As a general guidance, based on the risk/benefit balance assessment per the investigator, for a patient who experiences a new episode of Grade 3 hematological toxicity after more than 8 weeks following the last episode of same Grade 3 hematological toxicity, the investigator may consider resuming the patient on the same drug dose should the patient satisfy the following conditions:

- The patient showed stable hematological counts (Grade  $\leq 2$ ) during that timeframe
- In the absence of any signs or risk of infection
- The patient is benefiting from study treatment

If a patient requires administration of blood cell growth factors, the dose of study drug must be suspended for at least 48 hours after the last dose of blood cell growth factors was administered and until toxicity resolves to at least Grade 2, then reduced by 1 dose level as outlined in [Table JPBQ.9.3](#), if a dose reduction for the specific event necessitating the use of the growth factors has not already occurred.

Before re-initiation of blinded study drug, hematologic toxicity must resolve to at least Grade 2.

#### **9.4.1.1.4. Nonhematologic Toxicity**

If a patient experiences Grade  $\geq 3$  nonhematologic toxicity, then dosing must be suspended (until the toxicity resolves to either baseline or at least Grade 1) and the dose of blinded study drug must be reduced as outlined in [Table JPBQ.9.3](#).

If a patient experiences persistent or recurrent Grade 2 nonhematologic toxicity (except diarrhea; see Section 9.4.1.1.4.1 or ALT increased, refer to Section 9.4.1.1.4.2 ) possibly related to blinded

study drug that does not resolve with maximal supportive measures within 7 days to either baseline or Grade 1, then dosing must be suspended (until the toxicity resolves to either baseline or at least Grade 1) and the dose of blinded study drug must be reduced by 1 dose level as outlined in [Table JPBQ.9.3](#).

Before re-initiation of blinded study drug, nonhematologic toxicity (except alopecia and fatigue) must resolve to either baseline or at least Grade 1.

#### **9.4.1.1.4.1. Diarrhea**

A patient experiencing diarrhea requiring hospitalization (irrespective of grade, that is, requiring intravenous [IV] rehydration) or severe diarrhea (Grade 3 or 4; see [Attachment 9](#)) must have study treatment suspended (until the toxicity resolves to at least Grade 1) and must have the blinded study drug dose reduced by 1 dose level as outlined in [Table JPBQ.9.3](#).

If a patient experiences persistent or recurrent diarrhea that does not resolve with maximal supportive measures (refer to Section [9.6.5](#)) within 24 hours to at least Grade 1, then study treatment must be suspended (until the toxicity resolves to at least Grade 1) and the dose of blinded study drug must be reduced by 1 dose level as outlined in [Table JPBQ.9.3](#).

#### **9.4.1.1.4.2. Hepatic Toxicity**

Does modifications and management for increased ALT are provided in [Table JPBQ.9.2](#). For persistent or recurrent Grade 2 ALT increased that does not resolve with maximal supportive measures within 7 days to baseline or Grade 1, or Grade 3 ALT increased, blinded study drug must be suspended until the toxicity has resolved to at least Grade 1 and the dose must be reduced by 1 dose level. Discontinue blinded study drug for Grade 3 increased ALT ( $>5.0 \times$  ULN) with total bilirubin  $>2 \times$  ULN, in the absence of cholestasis. For Grade 4 ALT increased, the patient must be discontinued from blinded study drug. Refer to Section [10.3.3.1](#) for additional hepatic monitoring guidance.

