**Table JPBQ.9.2. Toxicity Dose Adjustments and Delays of Blinded Study Drug for Study JPBQ**

Toxicity Type	Toxicity Profile and Severity	Dose Suspension	Dose Reduction
Hematologic Toxicity Section 9.4.1.1.3	Grade 3	Dose MUST be suspended until toxicity resolves to at least Grade 2.	Dose MAY be reduced by 1 dose level at investigator's discretion.
Hematologic Toxicity Section 9.4.1.1.3	Recurrent Grade 3 within 8 weeks	Dose MUST be suspended until toxicity resolves to at least Grade 2.	Dose MUST be reduced by 1 dose level.
Hematologic Toxicity Section 9.4.1.1.3	Grade 4	Dose MUST be suspended until toxicity resolves to at least Grade 2.	Dose MUST be reduced by 1 dose level.
Hematologic toxicity: If patient requires administration of blood cell growth factors Sections 9.4.1.1.3 and 9.6.4	Regardless of severity (Use growth factors according to ASCO Guidelines)	Dose MUST be suspended for at least 48 hours after the last dose of blood cell growth factors was administered and until toxicity resolves to at least Grade 2.	Dose MUST be reduced by 1 dose level unless already performed for incidence of toxicity that led to the use of growth factor.
Nonhematologic Toxicity b (except diarrhea and ALT increased) Section 9.4.1.1.4	Persistent or recurrent Grade 2 that does not resolve with maximal supportive measures within 7 days to baseline or Grade 1	Dose MUST be suspended until toxicity resolves to either baseline or Grade 1.	Dose MUST be reduced by 1 dose level.
Nonhematologic Toxicity Section 9.4.1.1.4	Grade 3 or 4	Dose MUST be suspended until toxicity resolves to either baseline or Grade 1.	Dose MUST be reduced by 1 dose level.
Diarrhea Sections 9.4.1.1.4.1 and 9.6.5	Grade 2 that does not resolve within 24 hours to at least Grade 1	Dose MUST be suspended until toxicity resolves to at least Grade 1.	Dose reduction is NOT required.
Diarrhea Sections 9.4.1.1.4.1 and 9.6.5	Persistent or recurrent Grade 2 that does not resolve with maximal supportive measures, or any Grade of diarrhea that requires hospitalization	Dose MUST be suspended until toxicity resolves to at least Grade 1.	Dose MUST be reduced by 1 dose level.
Diarrhea Sections 9.4.1.1.4.1 and 9.6.5	Grade 3 or 4	Dose MUST be suspended until toxicity resolves to at least Grade 1.	Dose MUST be reduced by 1 dose level.

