ALT Increased (Sections 9.4.1.1.4.2. and 10.3.3.1)	Persistent or recurrent a Grade 2 (>3.0-5.0×ULN), or Grade 3 (>5.0-20.0×ULN) c	Dose MUST be suspended until toxicity resolves to baseline or Grade 1.	Dose MUST be reduced by 1 dose level.

ALT Increased (Sections 9.4.1.1.4.2 and 10.3.3.1)	Grade 4 (>20.0×ULN)	Blinded study drug MUST be discontinued.	Blinded study drug MUST be discontinued.
ALT Increased with increased total bilirubin, in the absence of cholestasis (Sections 9.4.1.1.4.2)	Grade 3 increased ALT (>5.0 × ULN) with total bilirubin >2 × ULN	Blinded study drug MUST be discontinued	Blinded study drug MUST be discontinued

Abbreviation: ALT = alanine transaminase; ASCO = American Society of Clinical Oncology.

Note: MUST = mandatory.

- a Determination of persistent events will be at the discretion of the investigator. Recurrent toxicity refers to the same event occurring within the next 8 weeks (as measured from the stop date of the preceding event). As a general guidance, based on the risk/benefit balance assessment per the investigator, for a patient who experiences a new episode of Grade 3 hematological toxicity after more than 8 weeks following the last episode of same Grade 3 hematological toxicity, the investigator may consider resuming the patient on the same drug dose should the patient satisfy the following conditions:
- shows stable hematological counts (Grade ≤2) during that timeframe
  - has absence of any signs or risk of infection
  - is benefiting from study treatment
- b Additional guidance for renal and hepatic monitoring is in Sections 10.3.3.1 and 10.3.3.2
- c Grade 3 ALT increased is a trigger for additional assessments and possibly hepatic monitoring. See Section 10.3.1.1 for additional guidance for hepatic monitoring

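### Section 9.4.1.1.4.2 restates the Grade 2 ALT dose rule with a 7-day condition, and a different end to suspension, that the mandatory ALT row of Table JPBQ.9.2 does not have

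*Protocol*

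**What the plan says.** Protocol Section 9.4.1.1.4.2 (Hepatic Toxicity) opens by naming the source of its rule: "Does modifications and management for increased ALT are provided in" Table JPBQ.9.2. It then requires suspension of blinded study drug and a one-level reduction for Grade 3 ALT and for "persistent or recurrent Grade 2 ALT increased that does not resolve with maximal supportive measures within 7 days to baseline or Grade 1". It ends the suspension at Grade 1 or better and does not mention baseline there.

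The ALT row of Table JPBQ.9.2 applies to persistent or recurrent "Grade 2 (>3.0-5.0×ULN), or Grade 3 (>5.0-20.0×ULN". It sets no time limit and no supportive-measures condition. Suspension and reduction are both marked MUST, and the table adds "Note: MUST = mandatory". Suspension lasts until ALT is back to baseline or Grade 1. Footnote a leaves persistence to the investigator and defines recurrence: "Recurrent toxicity refers to the same event occurring within the next 8 weeks (as measured from the stop date of the preceding event".

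Within the table, the 7-day wording stands only in the general Grade 2 nonhematologic row: "Persistent or recurrent Grade 2 that does not resolve with maximal supportive measures within 7 days to baseline or Grade 1". That row covers nonhematologic toxicity "except diarrhea and ALT increased". Section 9.4.1.1.4 makes the same exclusion and sends ALT readers to Section 9.4.1.1.4.2.

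**The concern.** A mandatory dose rule should read the same wherever a site finds it. Here the section adds a condition for ALT that the table keeps for other toxicities and withholds from ALT by name. A site that works from the hepatic section alone could keep the same dose where the table makes suspension and reduction compulsory. The same conduct would then agree with one part of the protocol and breach another. At stake is consistent handling of a liver-safety rule, and nothing in the statistical analysis.

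**Working it through.** The plan gives no figure to reproduce, so the check is a comparison of the two rules followed by simple arithmetic on their reach.

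**1. Triggers side by side**

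| Course of a Grade 2 ALT rise | Table JPBQ.9.2, ALT row | Section 9.4.1.1.4.2 |
|---|---|---|
| Persistent | Suspend and reduce; persistence is the investigator's call (footnote a) | Suspend and reduce if unresolved at 7 days; no demonstrable conflict, since the investigator may judge persistence by the same 7 days |
| Recurs within 8 weeks, still present after 7 days on maximal support | Suspend and reduce | Suspend and reduce (possibly up to 7 days later) |
| Recurs within 8 weeks, clears within 7 days | Suspend and reduce | Neither required, neither forbidden |

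The required action therefore differs in one situation, the last row. The recurrence window is 8 × 7 = 56 days.

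**2. Does another rule close the gap?** Section 9.4.1.1.2 says that for toxicity the "blinded study drug and/or NSAID/fulvestrant may be suspended or delayed" on the investigator's judgment. Its next paragraph does mandate a reduction when the same toxicity returns at the same or a higher grade, but only if that return requires a suspension. Whether this return requires one is what the table and the section answer differently, so the gap remains.

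**3. Size of the missed action** (dose levels from Table JPBQ.9.3)
- 150 to 100 mg Q12H: (150 − 100)/150 = 33.3%.
- 100 to 50 mg Q12H: (100 − 50)/100 = 50.0%.
- At 50 mg Q12H the default is discontinuation, subject to discussion with the sponsor physician (Section 9.4.1.1.1.1).

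These are dose steps, not estimates of trial impact.

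**4. Would scheduled tests show the case?** The inputs are from Attachment 1, as far as its table can be read: Day 15 ± 3 chemistry in Cycles 1 and 2, Day 1 chemistry in every later cycle, and Day 1 samples allowed up to 5 days early (footnote k). The next Day 1 is Day 29.
- Nominal gap: 29 − 15 = 14 days in Cycles 1 and 2; 28 days afterwards.
- Shortest gap in Cycles 1 and 2: (29 − 5) − (15 + 3) = 24 − 18 = 6 days.
- Shortest gap from Cycle 3 on: 28 − 5 = 23 days, which exceeds 7.

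From Cycle 3 on, clearance within 7 days can be shown only by an unscheduled test. Footnote k leaves local chemistry during a cycle to the investigator's discretion.

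**5. End of suspension.** The table accepts baseline or Grade 1, and the closing sentence of Section 9.4.1.1.4 also accepts baseline. Section 9.4.1.1.4.2 requires Grade 1 or better. The difference matters for a patient who enters above Grade 1. Inclusion Criterion 6 admits ALT up to 5 times ULN with liver metastases, and the table puts Grade 2 at more than 3.0 and up to 5.0 times ULN, so such a patient can start at Grade 2. She could restart at her baseline under the table but not under the section.

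**The case against.** The strongest reply is that the section names the table as its source, the table is mandatory, and a site that follows the table's trigger satisfies both. That stands, and it is why the point is minor. It does not remove the point: Section 9.4.1.1.4 sends ALT readers to the hepatic section, which then spells out its own, narrower trigger.

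A second reply is that the 7 days merely define persistence. Footnote a gives that judgment to the investigator, and the section applies the 7 days to recurrent rises as well, which footnote a defines by the 8-week window alone.

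A third is that the row lost text when the PDF was read. This is unlikely: the cell runs complete through both grade ranges, and the 7-day wording is intact in the general row.

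A fourth is that the case is rare and that section 9.4.1.1.2 already covers recurrence. Rarity stands. The cover is partial: it narrows the practical gap to recurrences that the investigator judges not to need suspension.

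A fifth concerns the remedy, and it stands. Striking the 7-day phrase alone would remove the only baseline qualifier in either Grade 2 ALT trigger and would leave the two endings of suspension different.

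A reader might infer more than the documents support. They do not show a conflict for persistent rises, for the reason in the working. The section does not forbid suspension or reduction. The actions for Grade 3 ALT (apart from the ending of suspension), Grade 4 ALT and ALT with raised bilirubin agree in substance. Nothing in the text shows which version the sponsor intended; the case for the table rests on its mandatory status and on the section's own reference to it.

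**Conclusion.** The inconsistency is real in the current text and is minor. It comprises one situation in which the required action differs (Grade 2 ALT that recurs within 8 weeks and clears within 7 days) and one difference in when suspension ends. In the first, the table mandates a step down of 33% or 50%, or by default discontinuation at the lowest dose, and the section requires nothing.

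The conclusion rests on footnote a governing the word recurrent in the ALT row, where its marker stands, and on the ALT row being complete as read. The remark that scheduled tests would seldom show the case rests on the reading of Attachment 1 above. The documents give no ALT event rates, so no patient count can be offered. A reader might infer a wider safety or efficacy consequence; the documents do not support one. Alpha, power, sample size and the PFS analysis are untouched.

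**What to change.** Replace the Grade 2 and Grade 3 sentence in Section 9.4.1.1.4.2 with the table's rule. For example: *Blinded study drug must be suspended for Grade 2 ALT that is persistent or recurrent, as defined in Table JPBQ.9.2 footnote a, and for Grade 3 ALT. It may restart, one dose level lower, once ALT has returned to baseline or Grade 1.* The rules for Grade 4 and for ALT with raised bilirubin stay as they are.

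Add that a Grade 2 value no worse than the patient's own baseline is not a trigger. Put this in both the section and a table footnote, so that no new mismatch arises. It protects patients with liver metastases who enter with ALT up to 5 times ULN.

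Aligning the section to the table is preferable to adding the 7-day condition to the table, because no ALT test is scheduled at 7 days with which to apply it.

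The cost is one sentence replaced and one clarification added at the next amendment, plus a memo to sites. The downside is a few more mandatory reductions for short recurrent Grade 2 rises at sites that had followed the section alone.

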### 9.4.1. Special Treatment Considerations

#### 9.4.1.1. Dose Adjustments and Delays

Toxicity dose adjustments and delays of blinded study drug for this study are summarized in [Table JPBQ.9.2](#).

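### For a patient with liver metastases who entered with ALT above 3 and up to 5 × ULN, Protocol 9.4.1.1.4.2 forbids the restart at baseline that Table JPBQ.9.2 permits

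*Protocol*

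**What the plan says.** Five parts of the protocol bear on this.

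- **Section 7.1, Inclusion Criterion 6.** ALT may be up to 3.0 × ULN at entry, or up to 5 × ULN if liver metastases are present.
- **Table JPBQ.9.2, ALT row.** Grade 2 is above 3.0 and up to 5.0 × ULN; Grade 3 is above 5.0 and up to 20.0 × ULN. For persistent or recurrent Grade 2, or Grade 3, the dose must be "suspended until toxicity resolves to baseline or Grade 1" and then reduced by one level.
- **Section 9.4.1.1.4, Nonhematologic Toxicity.** The paragraph on Grade 3 or worse ends the suspension at baseline or Grade 1. The section closes: "Before re-initiation of blinded study drug, nonhematologic toxicity (except alopecia and fatigue) must resolve to either baseline or at least Grade 1". ALT is excepted only in the paragraph on Grade 2.
- **Section 9.4.1.1.4.2, Hepatic Toxicity.** After pointing to the table for ALT management, it begins its own rule "For persistent or recurrent Grade 2 ALT increased that does not resolve with maximal supportive measures within 7 days to baseline or Grade 1", adds Grade 3, and concludes that "blinded study drug must be suspended until the toxicity has resolved to at least Grade 1", with a one-level reduction. Its restart clause does not mention baseline.
- **Section 9.4.1.1.2, Dose Suspension.** A general parenthetical on resuming within a cycle reads "assuming resolution to at least Grade 1 for non-hematological toxicity", also without baseline. The same section states: "Patients not recovering from toxicity within 14 days should be considered for discontinuation of the blinded study drug". A longer delay is allowed in exceptional circumstances if the investigator and the sponsor's physician agree.

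**The concern.** A patient can be eligible, and can start at the full 150 mg Q12H, with an ALT that already counts as Grade 2. If her ALT rises and settles back where it began, the table treats the toxicity as resolved. The section written specifically for ALT does not, and keeps blinded drug on hold until she falls below the value at which she was enrolled.

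Where liver metastases hold ALT near its entry level, that condition may never be met. Once 14 days have passed, discontinuation of blinded drug is to be considered unless a longer delay is agreed. Two sites could therefore handle the same patient differently, each with a passage of the protocol to cite. What is at stake is consistent dosing, and possibly loss of blinded drug, in a patient who is back at her eligible baseline.

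**Working it through.** No sample-size, power or alpha figure is involved. The check compares the restart rules for one patient.

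**Inputs.** Entry limit with liver metastases: 5 × ULN (Section 7.1). Grade 2 band: above 3.0 and up to 5.0 × ULN (Table JPBQ.9.2). Grade 1 therefore means at most 3.0 × ULN, the lower edge of that band. Dose levels: 150, 100 and 50 mg Q12H (Table JPBQ.9.3).

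**Example.** Liver metastases, entry ALT 4 × ULN, rise to 6 × ULN (Grade 3, no mandatory-stop condition), return to 4 × ULN.

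| Text | Hold ends at | Restart at 4 × ULN? |
|---|---|---|
| Table JPBQ.9.2, ALT row | baseline or Grade 1 | permitted, one level lower |
| 9.4.1.1.4, Grade 3 or worse, and re-initiation | baseline or Grade 1 | permitted, one level lower |
| 9.4.1.1.4.2 | Grade 1 (≤3 × ULN) | forbidden |

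**Grade 2 variant.** Entry 3.5 × ULN, rise to 4.8 × ULN lasting more than 7 days, return to 3.5 × ULN. The table permits restart and 9.4.1.1.4.2 forbids it. I do not rely on 9.4.1.1.4 here, because its Grade 2 paragraph sends ALT to 9.4.1.1.4.2.

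**Range.** The conflict covers every entry ALT above 3.0 and up to 5.0 × ULN, which is eligible only with liver metastases. At an entry ALT of 3.0 × ULN or less, baseline already meets the Grade 1 limit and the conflict does not arise.

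**Further fall required.** Gap = entry value − 3:
- entry 3.5: 0.5 × ULN (0.5/3.5 = 14%)
- entry 4: 1 × ULN (1/4 = 25%)
- entry 5: 2 × ULN (2/5 = 40%)

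These figures show how far below entry she must go; they do not measure clinical consequence.

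**Doses.** Only the time between reaching baseline and reaching 3 × ULN is in dispute. Each such day withholds 2 doses: 2 × 100 = 200 mg after a first reduction, or 2 × 50 = 100 mg after a second (placebo equivalents in Arms A2 and B2). The documents give neither the number of such days nor the number of such patients, so no total follows.

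**Inside 9.4.1.1.4.2.** Its Grade 2 clause counts return to baseline within 7 days as resolution, so that patient is never suspended. Its restart clause then leaves baseline out, so a patient back at the same value after a suspension stays off drug.

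**The case against.** The strongest reply is that the table governs. Section 9.4.1.1 says "Toxicity dose adjustments and delays of blinded study drug for this study are summarized in" the table, and 9.4.1.1.4.2 itself opens by pointing there. Section 10.3.3.1 lets ALT monitoring stop at approximate baseline levels. Section 9.4.1.1.2 describes toxicity as an event possibly related to study treatment, so an ALT elevation that predates treatment can be read as outside it. Most readers would probably settle on baseline. This stands as evidence of what was meant, but not as a rule: no passage gives the table precedence, and 9.4.1.1.4.2 goes on to state its own mandatory condition.

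A second reply is that a stricter restart rule for liver toxicity is defensible and may have been intended. The documents do not declare the intent, so this cannot be excluded. If it was intended, however, the table and 9.4.1.1.4 are the texts in error, and a correction is still needed.

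A reader might infer that sites face two opposite mandatory orders. The documents do not support that. The table and 9.4.1.1.4 set a minimum condition for ending the hold, and 9.4.1.1.2 says the investigator may resume. None of them commands a restart at baseline, so a site that waits for Grade 1 breaches nothing. The breach runs one way only: a restart that the table allows violates 9.4.1.1.4.2.

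**Conclusion.** The restart rule for ALT conflicts with itself in the current text and is wrong as written, at minor severity. The mismatch is certain. That baseline was meant to count is the better-supported reading, but remains an inference.

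The affected group is narrow: liver metastases, entry ALT above 3 and up to 5 × ULN, a qualifying ALT rise without a mandatory stop, a lower dose level normally still available, and a return to entry value without reaching Grade 1. Its size cannot be derived and is probably small. The sponsor's physician can agree a longer delay, and NSAI or fulvestrant may continue if blinded drug is stopped. A reader might go on to infer lost efficacy or an effect on the PFS comparison; with neither patient numbers nor days known, nothing in the documents supports that, and none is claimed. Power and type I error are untouched.

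**What to change.** In the restart clause of Protocol 9.4.1.1.4.2, insert the words *baseline or* before *at least Grade 1*, so that it matches the ALT row of Table JPBQ.9.2. Optionally, align the parenthetical in 9.4.1.1.2 for those nonhematologic toxicities where the table accepts baseline; diarrhea stays at Grade 1, where the table and its own section already agree.

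The table, the one-level dose reduction and the mandatory stops (Grade 4 ALT; Grade 3 ALT with bilirubin above 2 × ULN without cholestasis) do not change. Should the sponsor actually want Grade 1 for ALT, the alternative is to say so in the table and in 9.4.1.1.4.

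The cost is two words and one optional alignment at the next amendment, with no added tests, visits or patients.
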